3.4.1. Primary effectiveness endpoint

 The primary endpoint of change from baseline in the TBUT as rated by a masked rater at 4 weeks will be analyzed for non-inferiority using a margin of 2.5 seconds. The primary non-inferiority hypothesis set will be: Ho: $\mu_{\text{Tixel}} - \mu_{\text{Lipiflow}} + \delta \le 0$

HA: $\mu_{\text{Tixel}} - \mu_{\text{Lipiflow}} + \delta > 0$

where μ_{Tixel} and $\mu_{Lipiflow}$ are the mean TBUT changes from baseline at 4 weeks for Tixel and Lipiflow, respectively and $\delta=2.5$.

NoVoxel

A change in TBUT of at least 2.5 seconds in each group will be considered clinically significant.

The difference between Tixel and Lipiflow in changes from baseline in TBUT as rated by a masked rater at 4 weeks will be assessed using a linear mixed-effects model with a random effect for subjects and fixed effect for treatment and baseline score as covariate. The random-effect adjusts the "within-subject correlation" between eyes. Least square means will be estimated by treatment arm from the model. The confidence interval for the estimates will be one-sided and a test value of 2.5 will be used to test non-inferiority.

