3.4.2. Secondary effectiveness endpoints

- 1- OSDI
 - The change from baseline at 4 weeks and 12-weeks in the Ocular Surface Disease Index (OSDI) will be calculated along with 95% confidence interval. The Paired T-test or Signed rank test for two means (paired observations) (as is appropriate) will be applied for testing the statistical significance of the changes within each study group.
 - The two-sample T-test or Non-parametric Wilcoxon-Mann-Whitney Rank sum test for independent samples (as is appropriate) will be applied for testing the statistical significance of the difference in change from baseline in OSDI at week 4 between the study groups
- 2- MGS
 - The difference between Tixel and Lipiflow in changes from baseline in MGS as rated by a masked rater at 4 weeks and 12 weeks will be assessed using a linear mixed-effects model with a random effect for subjects and fixed effect for treatment and baseline score as covariate. The random-effect adjusts the "within-subject correlation" between eyes. Least square means will be estimated by treatment arm from the model.
- 3- TBUT

18-Jan-2023

Clinical Protocol Number: CLN 0858 Rev. 007

In 12 weeks, the follow-up visit will be analyzed in the same way as the 4-weeks follow-up visit.

3.4.3. Exploratory Analysis:

_

- For each follow-up (4 weeks and 12 weeks), if non-inferiority is achieved, the TBUT score change from baseline as rated by a masked rater at the relevant follow will be analyzed for superiority. The hypothesis set will be:
- Ho: $\mu_{Tixel} \mu_{Lipiflow} \le 0$
- HA: $\mu_{\text{Tixel}} \mu_{\text{Lipiflow}} > 0$

3.5.Handling of Missing data

Every effort will be made to complete follow-up for all patients and avoid missing data, in particular regarding the primary endpoint variable. However, in the event data is missing, multiple imputation will be used. Further details will be provided in the statistical analysis plan.

3.6.Interim Analysis

No interim analyses are planned for this study.

3.7.Sample Size Justification

55 patients will be enrolled in each treatment group.

Sample size rationale:

The sample size calculation is based on the primary efficacy endpoint. Specifically, the sample size calculation was based on the non-inferiority with a 2.5 second margin of the change from baseline in TBUT score as assessed by a masked rater at 4 weeks follow-up for Tixel versus LipiFlow. The expected standard deviation of the difference in change is 4.5 seconds.

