The calculation assumes the worst-case scenario that the TBUT of both subjects eyes subjects is completely correlated (r=1).

Sample size justification:

When the sample size in each group is 44, a two group one-sided 0.05 significance level t-test will have 80% power to reject the null hypothesis that the test and standard are not non-inferior (the difference in means, μ_T - μ_L , is 2.5 seconds or farther from zero in the same direction) in favor of the alternative hypothesis that the means of the two groups are non-inferior, assuming that the expected difference in means is 0 and the common standard deviation is 4.5 s.

Assuming a 20% drop-out rate, 55 patients will be enrolled in each group ensuring a sample size of 44 patients per group.

Novoxel

[4 -Dixon et al, 1983; 5 O'Brien et al, 1993]

3.8.Poolability Analysis

Patient demographic characteristics and background variables shall be summarized.

The primary endpoint analysis will be conducted for each investigational site. The justification for pooling all the data to estimate a common effect across study sites requires the homogeneity of response across study sites. An analysis of variance (ANOVA) of the differences will be generated to test whether the investigational sites differ with respect to primary study endpoint (only the site will be included in this analysis model). The test of inhomogeneity of response will be based on a two-sided significance test at the 0.15 level of significance. If the sites differ by this test, then a second analysis will be done including study site and all baseline characteristics that have P<0.10 in the analysis of baseline characteristics by site to understand if the imbalance in the primary endpoint between sites is related to an imbalance in baseline characteristics.

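### 12-week TBUT non-inferiority does not depend on the 4-week primary, so a formal 12-week verdict can follow a failed primary, and each type of TBUT claim has two unadjusted chances

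*Combined protocol and SAP*

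**What the plan says.** The primary test (section 3.4.1) is a single comparison of TBUT change, "at 4 weeks will be analyzed for non-inferiority using a margin of 2.5 seconds". Its interval is described without a confidence level: "The confidence interval for the estimates will be one-sided and a test value of 2.5 will be used to test non-inferiority".

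Change in TBUT at 12 weeks is a listed secondary endpoint in the synopsis. Its whole analysis rule, in section 3.4.2, is: "In 12 weeks, the follow-up visit will be analyzed in the same way as the 4-weeks follow-up visit". That carries over the non-inferiority test and margin, and it does not mention the 4-week outcome.

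Section 3.4.3, headed as exploratory, adds a one-sided superiority hypothesis with the condition "For each follow-up (4 weeks and 12 weeks), if non-inferiority is achieved". The test is then made at the visit that passed, so the gate works within a visit and not between visits.

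The only level given for a treatment comparison is in the sample-size text (synopsis and section 3.7): "a two group one-sided 0.05 significance level t-test". The supplied text contains no testing order, alpha split or multiplicity adjustment across visits. Section 3.1 leaves further detail to a statistical analysis plan to be finalised before database lock.

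**The concern.** This is a pivotal study meant to support an indication. If the 4-week primary fails, the plan as written still produces a 12-week non-inferiority verdict in the same form as the primary and, if that passes, a 12-week superiority test. It does not say what such a result would mean. With two visits and no link between them, each type of TBUT claim also has two chances, each at its own full level. What is at stake is the standing of the 12-week statements. The validity of the 4-week conclusion is not in question.

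**Working it through.** **Inputs from the documents.** Margin 2.5 s (3.4.1). From 3.7: one-sided 0.05, 44 analysable patients per group, and "the expected difference in means is 0 and the common standard deviation is 4.5 s". Both eyes are taken as fully correlated, so the patient is the unit.

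**Assumptions.** One-sided 0.05 applies to every TBUT test. The documents give no between-visit correlation r of the test statistics, so a range from 0 to 0.9 is shown. Normal approximation, critical value c = 1.645.

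**The plan's own figure.** n per group = 2 × (1.645 + 0.842)² × 4.5² / 2.5² = 40.1, so 41. An exact noncentral-t calculation also gives 41 (power 80.2%). The stated 44 gives 82.6% power (83.2% by the normal approximation) against the stated 80%. The gap is conservative and does not bear on this point. The dropout step reproduces: 44 / 0.80 = 55.

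**False non-inferiority, true difference −2.5 s at both visits.** Each test passes with probability 0.05. Let J(r) be the bivariate normal probability that both pass.

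- At least one false pass = 0.05 + 0.05 − J(r)
- Week 4 fails and week 12 alone falsely passes = 0.05 − J(r)

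| r | At least one false pass | Week 12 alone |
|---|---|---|
| 0 | 9.75% | 4.75% |
| 0.3 | 9.3% | 4.3% |
| 0.5 | 8.8% | 3.8% |
| 0.7 | 8.0% | 3.0% |
| 0.8 | 7.5% | 2.5% |
| 0.9 | 6.8% | 1.8% |

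At r = 0, J = 0.05² = 0.0025, so 0.10 − 0.0025 = 0.0975. The benchmark is 5% for the primary alone.

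**False superiority, true difference 0 at both visits.** The same formula gives the same 6.8% to 9.75%. The within-visit gate does not lower this, because any result that passes superiority also passes non-inferiority. The excess comes only from having two visits.

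**How often the situation arises under the plan's own assumptions.** With true difference 0 and 44 per group, the standard error is 4.5 × √(2/44) = 0.959 and 2.5 / 0.959 = 2.606. The primary fails with probability Φ(1.645 − 2.606) = 16.8%. Week 4 fails and week 12 passes in 14.0% of all trials at r = 0 (0.168 × 0.832), 11.8% at 0.3, 10.0% at 0.5, 7.8% at 0.7 and 4.5% at 0.9. At r = 0.5 that is 10.0 / 16.8, about 60% of the trials with a failed primary. With true difference 0 these passes are not false claims. They show how often the plan would yield a 12-week verdict whose status it does not define.

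**12-week superiority after a failed 4-week non-inferiority test, true difference 0.** By simulation: 0.84% at r = 0, 0.06% at r = 0.5, below 0.01% at r = 0.7 or more. The route is open but rarely taken.

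**With 12-week non-inferiority conditional on week 4.** If both non-inferiority nulls hold, a false claim requires week 4 to pass, so the chance of any is 0.05 whatever r is. If only the 12-week null holds, it is at most 0.05.

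**The case against.** The strongest reply is that nothing confirmatory is damaged. There is one primary test, and nothing done at 12 weeks changes its type I error. Superiority sits under an exploratory heading. This stands, and it sets the limits of the point.

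Four stronger readings may tempt a reader, and the documents do not support them.

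- *The trial's primary error rate is inflated.* It is not. The 6.8% to 9.75% includes the primary's own 5%, and what week 12 adds is 1.8 to 4.75 percentage points.
- *The 12-week tests have no error control.* Each test holds its own level. Only joint control over the two visits is missing.
- *Superiority is a confirmatory claim tested at one-sided 0.05.* The plan calls it exploratory and states no level for it or for the 12-week test. The 0.05 is carried over from the sample-size text. At one-sided 0.025, the chance of at least one false superiority result would be 4.5% at r = 0.5. Comparing 8.8% with 2.5% as the gain from ordering would also mislead, because it mixes ordering with a halved level. A strict order of all four tests at one-sided 0.05 leaves 4.2% to 5.0%.
- *A superiority claim after a failed primary is a likely outcome.* When the devices are equal it occurs in under 1% of trials.

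Two further replies have some force. A testing order may be set in the deferred analysis plan, which cannot be checked here. The rule that is written, however, applies to each follow-up separately, so the later plan would have to replace it. OSDI and MGS are also secondary endpoints without adjustment, and a rule for TBUT alone does not control error across them.

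The exploratory label does not cover 12-week TBUT non-inferiority. That is a listed secondary endpoint, tested as the primary is, and its status after a failed primary is undefined.

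**Conclusion.** The point holds as a gap in the testing rule for secondary and exploratory TBUT results. A formal 12-week non-inferiority verdict can follow a failed primary, and each type of claim has two unadjusted chances. With Tixel truly 2.5 s worse at both visits, at least one false non-inferiority pass occurs with probability 6.8% to 9.75% instead of 5%. This rests on two assumptions that the documents do not settle: that one-sided 0.05 applies to every test, and a between-visit correlation from 0.9 to 0. The 4-week primary and the sample size are unaffected. It is an inexpensive improvement worth making before database lock, and it does not threaten the main conclusion.

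**What to change.** Amend sections 3.4.2 and 3.4.3, or set the rule in the statistical analysis plan before database lock:

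1. State the one-sided level for 4-week TBUT non-inferiority in the analysis section.
2. Test 12-week TBUT non-inferiority formally only if 4-week non-inferiority is met, at that same level. Otherwise report the 12-week difference as an estimate with its confidence interval and no verdict.
3. Keep superiority exploratory at both visits. Allow it only after 4-week non-inferiority is met and, for week 12, after 12-week non-inferiority is met as well. Report it with two-sided 95% intervals and make no confirmatory claim.

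A strict four-step order with 12-week non-inferiority ahead of 4-week superiority is not needed. It would block the step from non-inferiority to superiority at week 4, which is nested and costs no alpha.

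The cost is wording only. The primary keeps its full alpha and the sample size does not change. The downside is that a failed 4-week primary leaves no formal 12-week verdict, even if the 12-week data look favourable.

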Sample size	Up to 110 patients (220 eyes), 55 patients per device to be enrolled at up to 6
	study sites in the US, will serve as sample size to investigate whether the Tixel
	C device is non-inferior to the LipiFlow system in terms of change in TBUT
	from baseline to 4 weeks following the last treatment.
	Sample size rationale:
	The sample size calculation is based on the primary effectiveness endpoint.
	Specifically, the sample size calculation was based on the non-inferiority with
	a 2.5 seconds' margin of the change from baseline in TBUT score as assessed
	by a masked rater at 4 weeks follow-up for Tixel versus LipiFlow. The
	expected standard deviation of the difference in change is 4.5 seconds.
	The calculation assumes the worst case scenario that the TBUT of both eyes
	of subjects are completely correlated (r=1).
	Sample size justification:
	When the sample size in each group is 44, a two group one-sided 0.05
	significance level t-test will have 80% power to reject the null hypothesis that
	the test and standard are not non-inferior (the difference in means, μ_T - μ_L , is
	2.5 s or farther from zero in the same direction) in favor of the alternative

	hypothesis that the means of the two groups are non-inferior, assuming that
	the expected difference in means is 0 and the common standard deviation is
	4.5 s.
	Assuming a 20% drop-out rate (a relatively high rate is currently assumed due
	to Covid-19 uncertainty), 55 patients will be enrolled in each group ensuring
	a sample size of 44 patients per group.
Inclusion Criteria	1. Age 22 years and older of any gender or race.
	2. Provision of written informed consent prior to study participation.
	3. Willingness and ability to return for all study visits.
	4. Reports dry eye symptoms for three months prior to the study.
	5. Ocular Surface Disease Index (OSDI) score between 23-79.
	6. Tear break-up time (TBUT) ≤ 10 seconds in both eyes.
	7. Agreement/ability to abstain from dry eye/MGD medications for the
	time between the treatment visit/s and the final study visit. Ocular
	lubricants are allowed if no changes are made during the study.
	8. Reports having to use artificial tears or lubricants regulatory over the
	past month to relieve dry eye symptoms.
	9. Meibomian gland obstruction in both eyes based on a total Meibomian
	Gland Secretion Score ≤ 12 in each eye.
	10. At least 15 glands in each lower eyelid should be expressible, with a
	sterile cotton swab, at the slit lamp.

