3.2. Analysis Populations

- Intent-to-Treat Population: The intent-to-treat (ITT) population includes all randomized patients. Patients will be analyzed as randomized.
- Per Protocol Population: The per protocol (PP) population includes all patients who performed the 4 weeks follow-up visit, completed all the treatments as randomized, and have no major protocol deviations. Patients will be analyzed as treated. The primary analysis population will be the per-protocol (PP) population.
- Safety Population: The safety population will include all treated patients. The safety population will be analyzed for all safety assessments. Patients will be analyzed as treated. A summary table of number (%) of patients in each analysis population/set will be provided.

3.3.Demographic and Baseline Characteristics

Descriptive statistics or frequency tabulation will be provided for demographic and baseline characteristics, such as age, gender, race, and ethnicity.

3.4.Effectiveness Analyses

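### The stated 80% power at 44 patients per group does not follow from the printed inputs, which give 82.6% at 44 and reach 80% at 41 (minor, conservative)

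*Combined protocol and SAP*

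**What the plan says.** The sample-size paragraph appears twice, in the synopsis and in section 3.7, with the same figures. Section 3.7 states: "When the sample size in each group is 44, a two group one-sided 0.05 significance level t-test will have 80% power". The synopsis makes the same claim ("significance level t-test will have 80% power to reject the null hypothesis that" the treatment is not non-inferior). The effect and variability inputs follow in the same sentence: "assuming that the expected difference in means is 0 and the common standard deviation is 4.5 s". The margin is 2.5 s, given in the sample-size rationale and as δ in section 3.4.1. Both places also assume, as a worst case, that a patient's two eyes are perfectly correlated (r=1).

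Enrolment is then derived from the 44: "Assuming a 20% drop-out rate, 55 patients will be enrolled in each group ensuring a sample size of 44 patients per group".

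**The concern.** Every input needed for the power of a two-sample t-test is printed, so the stated pair (44 per group, 80%) can be checked directly. It does not reproduce: the inputs give more than 80% at 44, and fewer than 44 for 80%.

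This calculation justifies the size of a pivotal non-inferiority trial. A reader who recomputes it will get a different answer, and the text does not explain the gap. What is at stake is the traceability of the figure. The discrepancy runs in the safe direction, so neither the validity of the test nor the adequacy of enrolment is in doubt.

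**Working it through.** **Inputs**
- Test and level: two-group t-test, one-sided 0.05 (synopsis; section 3.7)
- Margin: 2.5 s (synopsis; sections 3.4.1 and 3.7)
- True difference: 0 (synopsis; section 3.7)
- Common SD: 4.5 s (synopsis; section 3.7)
- Between-eye correlation: 1, so the second eye adds no information and n counts patients
- Allocation: 1:1 (synopsis, randomization)

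**The plan's own steps**

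The drop-out step reproduces: 44/(1 − 0.20) = 55. The power step does not, as shown next.

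**Formula**

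Standard error = 4.5 × √(2/n); noncentrality = 2.5/standard error; degrees of freedom = 2n − 2. Power is the probability that a noncentral t variable exceeds the one-sided 0.05 critical value.

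**At n = 44**

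Standard error = 4.5 × √(2/44) = 0.959 s. Noncentrality = 2.5/0.959 = 2.606. With 86 degrees of freedom the critical value is 1.663. Power = 0.8265, that is 82.6%. The normal approximation gives 83.2%.

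**Smallest n for 80%**

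| n per group | Exact t power |
|---|---|
| 40 | 79.3% |
| 41 | 80.2% |
| 44 | 82.6% |

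The normal approximation agrees: n = 2 × (z₀.₉₅ + z₀.₈₀)² × 4.5²/2.5² = 40.06, which rounds up to 41.

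**Could another reading of the text give 80% at 44?** Two were tested, each changing one thing:
- One-sided 0.025 instead of 0.05: power at 44 is 73.1%, and 52 per group would be needed.
- 4.5 s taken as the SD of a between-arm difference, as one sentence in the text could suggest ("The expected standard deviation of the difference in change is 4.5 seconds"): the common SD becomes 4.5/√2 = 3.18 s and power at 44 is 97.8%.

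Neither gives 80%.

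**What the gap means for attrition**

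From 55 enrolled per group, 80% power holds until 41 evaluable remain: 55 − 41 = 14 losses, or 14/55 = 25.5%. The plan allows for 55 − 44 = 11 losses, or 20%.

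**The case against.** The strongest reply is that the sentence reports a target that has been met. It does not claim that 44 is the smallest adequate number, and 44 does give at least 80%. On that reading nothing is false, the gap is 2.6 points in the safe direction, and no decision in the trial depends on it. This reply largely stands on materiality and is why the point is minor. It does not remove the point: the text gives 80% as the power, does not say at least, and presents 44 as the number that enrolment must secure.

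A reader might go further and infer that an undisclosed input was used, for instance a larger SD. The documents do not support this. They print 4.5 s consistently, and back-solving does not single out one cause: with the other inputs held fixed, an SD of about 4.68 s or a margin of about 2.40 s would each give 80% at 44. Neither figure appears anywhere in the plan. The origin of 44 cannot be recovered from the text.

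A reader might also treat the loose wording nearby as part of the error. The sample-size null is written without a sign ("2.5 seconds or farther from zero in the same direction"), and 4.5 s carries two labels. Neither changes a result. The signed hypotheses in section 3.4.1 fix the direction, and the t-test sentence itself names 4.5 s as the common SD. Likewise, the decision sentence in section 3.4.1 could spell out its rule more fully, but that has no bearing on the power figure.

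**Conclusion.** The point holds as a minor, conservative reporting error. On the plan's printed inputs, power at 44 per group is 82.6%, not 80%, and 80% is reached at 41. This rests on taking 4.5 s as the common SD of the change from baseline, on r=1 between eyes, and on the t-test that the plan names. It says nothing about the power of the baseline-adjusted mixed model planned for the analysis.

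It would be wrong to conclude that the trial is underpowered: on its own assumptions it has slightly more power than it claims. Nor does the result argue for a smaller trial. The primary analysis uses the per-protocol population, whose members must have "completed all the treatments as randomized, and have no major protocol deviations", while the 20% allowance is described only as drop-out. The 3 patients per group between 41 and 44 are a modest reserve for those further exclusions.

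**What to change.** In the synopsis and in section 3.7, restate the power as about 83% at 44 evaluable patients per group, and add that 80% needs 41. Keep 55 enrolled per group, the 2.5 s margin, the one-sided 0.05 level and the analysis model. Keep the SD at 4.5 s as well: it should not be altered after the fact to make 44 fit.

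Optional in the same edit, and not needed to correct the error: write the sample-size null as μ_T − μ_L ≤ −2.5 s to match section 3.4.1, use the common-SD label throughout, and spell out the non-inferiority decision rule in section 3.4.1.

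The cost is a change of wording in two places.

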1. STUDY SYNOPSIS

Study Name	A Randomized, Masked (Evaluator), Controlled, Prospective Study
	evaluating the Effectiveness and Safety of the Tixel [®] Medical Device,
	Versus LipiFlow [®] in the Treatment of Meibomian Gland Dysfunction
Study Device	Tixel C
Stage of	Pivotal study to support an indication for use of treatment of Meibomian
Development	Gland Dysfunction
General Design	The study includes 2 stages: stage 1 is the main pivotal protocol, and stage 2
	is an extension study for a sub-group population which completed the main
	protocol, was treated with the Tixel device and meets specific criteria of
	clinical benefit (specified in the description of stage 2 below).
	Stage 1- the main protocol
Design	• Randomized, open-label study comparing the Tixel device to
	LipiFlow System.
	• Up to 110 patients (220 eyes) to be randomized in up to 6 clinical sites
	in the United States.
	• Evaluators will be masked as to the randomization assignments.
	• Both eyes will receive the same randomized assignment and both eyes
	of each patient will be evaluated at all time points.
	• Data from both eyes will be using in the statistical analysis.
	The random-effects model adjusts the standard error (SE) and the confidence
	interval (CI) for within-person correlation between eyes.
Objective	Evaluate the safety and effectiveness of the Tixel C device in adults with
	Meibomian Gland Dysfunction (MGD).
Primary	Change from baseline to the 4-weeks follow-up exam in Tear Break Up Time
Effectiveness	(TBUT).
Endpoint	
Secondary	• Change from baseline in patient symptoms using Ocular Surface Disease
Effectiveness	Index (OSDI) at 4-weeks and 12-weeks follow-up exam.
Endpoints	

	• Change from baseline to 4-weeks and 12-weeks follow-up exam in
	Melbomian Gland Score (MGS).
	• Change from baseline to 12-weeks follow-up exam in Tear Break Up Time
	(TBUT).
Key Safety	Comparison of the incidence of Ocular Adverse Events for the two treatment
Endpoint	arms.
Secondary Safety	• The evaluation of discomfort and pain during treatment.
Endpoints	• Changes from baseline following treatment for the test and control devices
	for the following assessments:
	° Ocular Surface Staining.
	° Intraocular Pressure.
	° Best corrected distance Visual acuity.
Population	Adult patients with symptoms of evaporative dry eye/MGD who do not
	respond adequately to conservative treatment options such as ocular
	lubricants.

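### The poolability test in section 3.8 fits site alone, so it does not test whether the Tixel-LipiFlow difference is the same at every site

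*Combined protocol and SAP*

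**What the plan says.** Section 3.8 (Poolability Analysis) states its purpose: "The justification for pooling all the data to estimate a common effect across study sites requires the homogeneity of response across study sites". It then sets out three steps.

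- By-site results: "The primary endpoint analysis will be conducted for each investigational site". No comparison of these results and no decision rule is given.
- Formal test: "An analysis of variance (ANOVA) of the differences will be generated". The aim and the model are given as follows: "to test whether the investigational sites differ with respect to primary study endpoint (only the site will be included in this analysis model"). On the level: "The test of inhomogeneity of response will be based on a two-sided significance test at the 0.15 level of significance".
- If the test rejects: a second analysis with site and those baseline characteristics that differ by site at P<0.10, "to understand if the imbalance in the primary endpoint between sites is related to an imbalance in baseline characteristics". Treatment is not named as a term.

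The primary model in section 3.4.1 has a "random effect for subjects and fixed effect for treatment and baseline score as covariate", with no site term. The synopsis plans up to 110 patients "to be randomized in up to 6 clinical sites". No treatment-by-site test appears anywhere in the supplied text.

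**The concern.** The common effect that pooling is meant to estimate is the between-arm difference in mean TBUT change, which is what the hypotheses in section 3.4.1 concern. Homogeneity of that effect is a question about treatment-by-site interaction. A one-way ANOVA on site asks something else: whether average TBUT change, over both arms, differs between sites. Sites can differ in that average (rater habits, case mix) while sharing one treatment difference. They can also have the same average while the treatment difference varies.

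So the test offered as the justification for pooling may raise an alarm when pooling is sound and stay quiet when it is not. The second-step model, as worded, seeks to explain site differences in the endpoint and also names no treatment term. In a pivotal study, a reader who relies on this result as evidence of a consistent treatment difference would be misled.

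**Working it through.** The plan states no figure on this point, so there is nothing to reproduce. The check has two parts: what the test can mean, and how it behaves.

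**1. What is being analysed.** Section 3.8 does not define the differences entering the ANOVA. Patients are randomized 1:1 and both eyes receive the same assignment, so the arms are unpaired. If the term meant between-arm differences, six sites would give six values. A model with a site factor would use 5 degrees of freedom for site and leave 6 − 1 − 5 = 0 for error. The workable reading is change from baseline, analysed over both arms. This agrees with the sentence's own reference to the primary endpoint, which section 3.4.1 defines as that change.

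**2. Inputs.**

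- From the documents: SD 4.5 s (variance 20.25) and 44 evaluable patients per group (section 3.7); level 0.15 (section 3.8); up to 6 sites (synopsis).
- Assumed: 6 equal sites with n = 7 per arm (84 patients, near the planned 88), one value per patient, and the site patterns below.

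The site-only F test has 5 and 78 df. The treatment-by-site F test has 5 and 72 df.

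**3. Constant treatment difference, site means varying with SD τ.** The site-only F statistic is inflated by 1 + 14τ²/20.25.

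- τ = 1 s: factor 1.69, flagged 43%.
- τ = 2 s: factor 3.77, flagged 81%.

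The treatment-by-site test stays at about 15% in both cases.

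**4. Treatment difference alternating ±d, site means equal.** The interaction noncentrality is (n/2)·Σd²/20.25.

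- d = 2.5 s: 3.5 × 6 × 6.25/20.25 = 6.48, power 65%.
- d = 5 s: 3.5 × 6 × 25/20.25 = 25.9, power 99.6%.

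The site-only test sees equal site means. The unmodelled arm differences go into its residual, whose expected mean square rises by 84(d/2)²/78.

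- d = 2.5 s: 20.25 + 1.68, flagged 12%.
- d = 5 s: 20.25 + 6.73, flagged 6%.

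Both are below the nominal 15%.

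**5. Only the Tixel response varies, by ±2.5 s.** Site means then move by ±1.25 s, and the site-only noncentrality is 14 × 6 × 1.25²/20.25 = 6.48. This is the same value as when both arms shift together by ±1.25 s with no heterogeneity at all.

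**6. Simulation, 20,000 trials per scenario (share flagged at 0.15).**

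| Scenario | Site-only | Treatment-by-site |
|---|---|---|
| No site or interaction effect | 14.8% | 14.9% |
| Constant difference, site SD 1 s | 43.0% | 14.6% |
| Constant difference, site SD 2 s | 81.5% | 15.1% |
| Difference ±2.5 s, equal site means | 11.8% | 65.8% |
| Difference ±5 s, equal site means | 5.8% | 99.6% |
| Tixel only ±2.5 s | 61.2% | 65.4% |
| Both arms ±1.25 s, constant difference | 65.2% | 15.1% |

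The last two rows show the problem most plainly. The planned test flags real heterogeneity and a harmless shift about equally often (61% and 65%).

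**7. Sensitivity to site layout (site-only versus treatment-by-site).**

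- 4 sites of 11 per arm: 46% or 80% versus 15% for site SD 1 or 2 s; 12% or 7% versus 76% or 99.9% for ±2.5 or ±5 s.
- Unbalanced sites of 14/10/8/6/4/2 per arm: 42% or 79% versus 15%; 12% or 6% versus 66% or 99.6%.

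**The case against.** The strongest reply has five parts.

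- **Meaning of the term.** Elsewhere in the statistical text a difference usually means the between-arm contrast, and the ANOVA sentence comes shortly after the plan for by-site primary analyses. Site-specific contrasts could be compared using their standard errors. That would be a weighted heterogeneity test, however, not an ANOVA with site as its only term, and it sits badly with the reference to the primary endpoint. The point shows that the wording is loose; it does not rescue the test.
- **Second step.** Treatment is unnamed there, not expressly excluded. This is correct, and the criticism should be put that way.
- **Deferral.** Section 3.1 leaves further details to the statistical analysis plan. But section 3.8 does not leave this model open: it says site alone is included.
- **Dependence on pattern.** The starkest contrast needs treatment differences that reverse sign around equal site averages. When only the Tixel response varies, the interaction test detects hardly more. Over-flagging also shrinks with small site effects: at a site SD of 0.5 s the planned test flags 22%. All of this stands. It limits the claim about lost sensitivity, but a flag still cannot be interpreted.
- **Consequence.** The test gates nothing, and by-site treatment differences will be shown anyway. This also stands and sets the severity. With about 7 evaluable patients per arm per site and no rule for comparing them, those displays do not replace a test of the stated question.

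**Conclusion.** The concern holds. The one formal test in section 3.8 compares average TBUT change between sites and does not test homogeneity of the Tixel-LipiFlow difference. That conclusion follows from the model terms and does not depend on the simulation.

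The size does rest on assumed site layouts and effect patterns, with the plan's SD and level. Across the three layouts and site SDs of 1 to 2 s, the planned test flags 42% to 81% of trials that have a constant treatment difference. It flags 6% to 12% when the difference alternates by ±2.5 or ±5 s around equal site means. Where only one arm's response varies it is about as sensitive as the interaction test, but its result is ambiguous.

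This should be fixed as a correction to a supportive analysis. The non-inferiority estimate and its error rate are not affected.

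**What to change.** In section 3.8, replace the site-only ANOVA with the section 3.4.1 mixed model (random subject, treatment, baseline TBUT) plus site and treatment-by-site, and test the interaction at the existing 0.15 level. If it is significant, keep treatment and treatment-by-site in the second-step model alongside the selected baseline characteristics. In either case, present the already planned site-specific differences with confidence intervals.

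The cost is wording and model terms, with no extra data or patients. The drawback is limited power: about 65% for a ±2.5 s alternation with 6 sites, even at the relaxed level. The plan should therefore say that a non-significant interaction does not prove homogeneity and that the site-specific estimates must still be read.
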